CRR	Complete Response Rate
CSR	Clinical Study Report
CT	Computed Tomography
CTCAE	Common Terminology Criteria for Adverse Events
DoCR	Duration of Complete Response
DoR	Duration of Response
ECG	Electrocardiography
ECOG	Eastern Cooperative Oncology Group
eCRF	Electronic Case Report Form
EU	European Union
FACT-Lym	Functional Assessment of Cancer Therapy–Lymphoma
FL	Follicular Lymphoma
γ GT	Gamma Glutamyl Transferase

HAMA	Human Anti-Murine Antibody / Human Anti-Mouse Antibody
HLA	Human leucocyte antigen
IRC	Independent Review Committee
ITT	Intent-To-Treat
LDH	Lactate Dehydrogenase
MBq	Mega Becquerel
MedDRA	Medical Dictionary for Regulatory Authorities
N/A	Not Applicable
NAb	Neutralising Antibody
NE	Not Evaluable
iNHL	indolent Non-Hodgkin Lymphoma
ORR	Overall Response Rate
OS	Overall Survival
PD	Progressive Disease
PFS	Progression-free Survival
PET	Positron-emission Tomography
PK	Pharmacokinetic
PR	Partial Remission
PT	Preferred Term
QoL	Quality of Life
RoW	Rest of World
SAE	Serious Adverse Event
SAF	Safety Analysis Set
SAP	Statistical Analysis Plan
SCT	Stem Cell Transplant
SD	Stable Disease
SI	International System of Units

SOC	System Organ Class
SPECT	Single Photon Emission Computed Tomography
SRC	Safety Review Committee
TEAE	Treatment Emergent Adverse Event
TFLs	Tables, Figures and Listings
WHO	World Health Organization

1 Introduction

This abbreviated statistical analysis plan (SAP) details the proposed analyses to be conducted by Veristat for the LYMRIT-37-01 phase I/II study (Part B) and the phase IIa expansion part (Part C).

Part A, dedicated to assessing the safety of various doses/regimens, was analysed under a separate SAP, Veristat study no: NOR18001.

In July 2022, LYMRIT-37-01 Part B and Part C were both terminated following slow recruitment. An ad hoc efficacy review of 61 patients (July 2022) who had received a dose of “40/15” and also had an Independent Review Committee (IRC) evaluated baseline and 3 month scan and efficacy assessment was conducted. Following this, the decision was taken to terminate the study. Details of this interim analysis are documented separately.

This analysis will be restricted to:

To support the final (close out) CSR, the efficacy and safety will be evaluated at a minimum of 3 months follow-up after the final patient has received the “40/15” regimen in Part B.

Specifically, this means that the following data will be formally analysed:

Table 1: Data to be reported: Analysis datasets and TFL’s to be produced

Category	Data	Comments
Demography and baseline information	Demographics	
	Disposition	
	Eligibility	Includes reasons for screening failure
	Med history	diagnosis of NHL (part C patients)
	Med history	diagnosis of FL (part B patients)
	Med history	general med history, listing only, no summaries required
	Prior and con meds	Prior meds, listing only, no summaries required
	Prior and con meds	Previous treatment for FL (part B), iNHL (part C)
Efficacy endpoints to be summarised are: ORR, CRR, DoR, DoCR and PFS from IRC assessment	Tumour visit response	From IRC: ORR, CRR, DoR, DoCR, PFS
Exposure data	Exposure	
Safety (AE and laboratory data) data	AE	
	Biochem	Listings only, no summaries required

	Haematology	Both listings and summaries required
--	-------------	--------------------------------------

OS variables will not be derived.

For all other data no formal TFL outputs are required. For all data in the table below, SAS datasets of the raw data should be supplied to Nordic Nanovector.

Table 2: Data for which only SAS raw data sets are required

Data table	Comments
AE SI	
Dna damage	DNA damage (Date/time) is this available?
ECG	ECG data only collected at baseline
Genomic biomarkers	Sample collection for genomic biomarkers
Imaging	Spect/CT evaluation
Immunological assessment	Protein Electrophoresis
Lab test results	Pregnancy test
Phys exam	Physical exam at baseline and through trial
PK concentrations	PK sampling times
Prior and con meds	Previous treatment for iNHL
Prior and con meds	Further anti-cancer therapies
Prior and con meds	Concomitant medications
Prior and con procedures	
Questionnaire	ECOG
Questionnaire	FACT-Lym
Response	Response following CT and PET assessments
SAE	
Serology sample	Sample collection for serology, hep B hep C HIV
Subject characteristics	Confirms randomisation and dose
Tumour identification	Biopsy tumour tissue - sample date, site, slides
Tumour identification	Target lesions (screening & follow-up)
Tumour identification	Non-measurable lesions (screening & follow-up)
Tumour identification	New lesions
Tumour identification	Bone marrow (screening & follow-up)
Tumour identification	PET (screening & follow-up)
Vital signs	Screening & follow-up
Immunological assessment	ADA (Date/time of sample)

Immunological assessment	HAMA (Date/time of sample)
Immunological assessment	Immunoglobulin (Date/time of sample)
Immunological assessment	Lymphocyte (Date/time of sample)

2 Study Design, Objectives and Endpoints

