5.3.2 Secondary Objectives

To compare the “40/15” and “100/20” treatment regimens in the randomised section and to evaluate the treatment regimen selected for further development, in terms of the following:

Efficacy

- ORR by investigator assessment
- Complete response rate (CRR) by independent review and investigator assessment
- DoR by independent review and investigator assessment
- Duration of complete response (DoCR) by independent review and investigator assessment
- PFS by independent review and investigator assessment
- OS

Safety

- To characterise the safety profile of Betalutin

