
DoR is the time from when criteria for response (CR or PR) is first met to the time of relapse or progression. Patients who have not relapsed/progressed will be censored at the last adequate tumour assessment.

Duration of Complete Response (DoCR)

DoCR is the time from when the complete response is first observed to the time of relapse. Patients who have not relapsed will be censored at the last adequate tumour assessment.

Overall survival (OS)

OS is defined as the time from administration of Betalutin to the date of death from any cause. Patients still alive or lost to follow-up are censored at the last date they were known to be alive. Patients still alive are censored at the last known date alive.

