14.2 Analysis for Patients in Part B with FL

The statistical analysis for Part B (in relation to the current single-arm design) will be performed at the following timepoints after last patient has been dosed with Betalutin:

- After all patients have had at least one post-treatment tumour assessment: This will consist of the baseline data, efficacy data on ORR, CRR and preliminary assessment on the longer-term efficacy outcomes (DoR, DoCR), and selected safety data. No change to the trial conduct nor the statistical analysis plan is envisaged.
- 9 months post Betalutin administration (6-month follow up of response for all patients with PR or CR): This will consist of the baseline data, efficacy data on ORR, CRR and preliminary assessment on the longer-term efficacy outcomes (DoR, DoCR, PFS, OS), and all safety data accumulated to this point.

- 15 months post Betalutin administration (12-months follow up of response for all patients with PR or CR): This will include updated analysis on the longer-term efficacy outcomes (DoR, DoCR, PFS and OS) and updated long-term safety data.
- 5 years: Final analysis will include long-term efficacy outcomes and safety data.

Pharmacokinetics, immunogenicity and biomarker assessments may be analyzed subsequently and reported in individual analytical reports as addendum to the Clinical Study Report(s). Exploratory biomarkers analysis will be published if relevant.

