3.5.2 Participant Disposition

A summary of participant disposition will be provided. This summary will present number of participants applicable to each of the following:

- Screened set, including screen-failures with reason.
- SAF.
- Efficacy Analysis Set.
- Gave consent for genomic biomarker analysis of tumour tissue (listing only).
- Gave consent to HLA typing (listing only).
- Gave consent for taking part in PK assessments (listing only).
- Gave consent for taking part in dosimetry assessments (listing only).
- Participants who completed the treatment period. (was in study up to Day 92).
- Participants who discontinued during the study treatment period (up to Day 92) (with summary of reasons for withdrawal from the Completion / Withdrawal eCRF page).
- Participants who discontinued after the study treatment period (from Day 93 onwards) (with summary of reasons for withdrawal from the Completion / Withdrawal eCRF page).

The treatment period is from Day 1 to Day 92 inclusive.

All duration derivations (months) are calculated relative to the date of first Betalutin administration using the following formula:

$$\text{Time to data cut off/death/withdrawal (months)} = ([\text{date of data cut off/death/withdrawal} - \text{date of first Betalutin administration}] + 1) * 12 / 365.25$$

For all summaries except the screened summary, the denominator for the percentages of participants in each category will be the number of participants in the SAF. The denominator for the percentages of participants for the screened summaries will be the number in the screened set.

Descriptive statistics for the duration of follow-up (months) will also be included where:

$$\text{Duration of follow-up (months)} = ([\{\text{latest date participant is known to be alive}\} - \text{date of first Betalutin administration}] + 1) * 12 / 365.25 \text{ rounded to 1 decimal place.}$$

Where latest date known to be alive is obtained using all data available for the participant (i.e. eCRF (including unscheduled), response and survival follow-up data).

Completion and withdrawal data, membership of each of the analysis sets along with reasons for exclusion will be listed.

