3.7.4 Secondary Endpoint: Progression-free survival (PFS)

3.7.4.1 Definition

PFS is defined as the interval from Betalutin administration and date of:

- Relapse (new or enlarged lesions after CR).
- Progression (new or enlarged lesions after PR or SD).
- Death from any cause.

Documented disease progression is defined as a Relapse (after CR) or progression (after PR or SD) and is indicated at the earliest date when the response assessment is given as progressive disease (PD). Death from any cause includes deaths occurring before the first post-baseline tumour assessment. If death occurs after two or more missed tumour assessments the participant should be censored (see below). PFS for participants meeting the events definition will be derived as follows:

$$\text{Progression-free survival time (months)} = ([\text{earliest of (First date of documented disease progression or death)} - \text{date of Betalutin administration}] + 1) * 12 / 365.25.$$

If none of the above events are observed PFS will be censored as follows:

- Incomplete/no baseline tumour IRC assessments: censor at date of Betalutin administration (study day 1).
- No documented disease progression: censor at date of last tumour IRC assessment where progression was not shown.

- Death or progression after two or more missed tumour assessments: censor at date of last tumour assessment where progression was not shown.

PFS for censored participants will be derived as:

$$\text{Progression-free survival time (months)} = ([\text{Date of censoring} - \text{date of Betalutin administration}] + 1) * 12 / 365.25$$

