3.8.2 Deaths

Deaths will be listed from the Death Report form showing date and cause of death.

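### Overall survival, a Part B secondary endpoint, is left out of the SAP without a specific reason, although the dates it needs are already specified there

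*SAP*

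**What the plan says.** **Protocol.** Section 5.3.2 sets out to compare the two regimens and "to evaluate the treatment regimen selected for further development, in terms of the following"; the list that follows includes OS. Section 5.6 repeats OS as a secondary efficacy endpoint. Section 14.1.7 defines it: "OS is defined as the time from administration of Betalutin to the date of death from any cause". The censoring rule is that "Patients still alive or lost to follow-up are censored at the last date they were known to be alive". Section 14.2 names OS at the 9-month analysis, among the "longer-term efficacy outcomes (DoR, DoCR, PFS, OS", and again at 15 months. The 5-year analysis covers long-term efficacy outcomes in general. The first look, after one post-treatment scan, names neither OS nor PFS.

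**SAP.** The Introduction, below Table 1, says "OS variables will not be derived", and OS is absent from the objectives and endpoints in Sections 2.2 and 2.3. Section 3.5.2 still specifies a time in months from first Betalutin to data cut-off, death or withdrawal, and a duration of follow-up from first Betalutin: "Where latest date known to be alive is obtained using all data available for the participant", survival follow-up data included. Section 3.8.2 provides the mortality output: "Deaths will be listed from the Death Report form showing date and cause of death". Section 3.10 attributes the considerable changes from the protocol to early termination and does not mention OS.

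**The concern.** A protocol secondary endpoint disappears from the analysis that supports the final study report. The documents describe no later analysis that would report it. Protocol Section 14.1.5 expects the SAP to document changes from the planned analyses, and a reader of Section 3.10 cannot tell why OS was removed while PFS was kept.

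At stake is a plain account of how long treated patients lived. Without it, the report can give individual death dates and descriptive follow-up, but no survival estimate that allows for unequal follow-up. Survival status is also not named among the raw datasets in SAP Table 2, so the SAP does not point to an alternative route to the result.

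**Working it through.** Neither document gives an OS sample size, event count or power, so there is no planned OS figure to reproduce. The check is a comparison of text, followed by an illustration of precision.

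**1. Are the ingredients of OS already in the SAP?**

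| Needed for OS (protocol 14.1.7) | Specified in SAP 3.5.2 |
|---|---|
| Origin: Betalutin administration | Date of first Betalutin administration |
| Event time: date of death, any cause | (date of death − first Betalutin + 1) × 12 / 365.25 |
| Censoring time: last date known alive | (latest date known alive − first Betalutin + 1) × 12 / 365.25 |

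Origin, event time and censoring time all match. SAP Section 2.1.1 also still describes survival follow-up that collects OS. Derivation is not the obstacle.

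**2. Where do deaths appear in the retained outputs?**

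- *PFS (SAP 3.7.4.1)* counts the earlier of progression or death, so a death after documented progression adds nothing. In addition, "If death occurs after two or more missed tumour assessments the participant should be censored".
- *DoR and DoCR (SAP 3.7.3.1)* count death, but only in responders and only if relapse has not come first. The missed-scan rule is not written into these definitions, so a responder's death after missed scans would count there.
- *Adverse events (SAP 3.8.1, Table 6).* Fatal events map to Grade 5, but the table by grade stops at Day 92. Serious TEAEs are tabulated from Day 1 onwards. However, protocol Section 13.2 limits reporting after 12 weeks to AESIs and treatment-related events, and Section 13.1.3 excludes deaths from disease progression from the SAE definition.
- *Disposition (SAP 3.5.2)* summarises withdrawal reasons up to Day 92 and from Day 93. Protocol Section 8.1 treats death as a withdrawal, so deaths are probably counted here. The eCRF page is not shown, so this is an inference. A count by reason is not a rate and does not allow for follow-up time.

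A late death after progression therefore reaches the listing and probably a disposition count, and nothing else.

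**3. Does immaturity explain the omission?**

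The SAP analysis is set at a minimum of 3 months after the last 40/15 patient is treated. The protocol's nearest look names neither PFS nor OS. The SAP nevertheless keeps PFS, with rates at 3, 6, 9, 12 and 15 months and a Kaplan-Meier plot (3.7.4.1.1). Immaturity would apply to both endpoints.

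Potential follow-up is probably longer than 3 months for many patients. The 47 interim patients already had at least 3 months of observation before Version 14 (protocol 4.8.10). Version 15 cites the position as of January 2021 (4.8.6), and the study stopped in July 2022. That suggests more than a year for some patients. It is an inference, because treatment dates are not given.

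**4. How precise would an OS rate be?**

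Assumptions: no censoring before the landmark; the true rate is not in the documents, so a range is shown; n = 61, the 40/15 patients in the July 2022 review (SAP Introduction). Exact limits for x survivors of n are the 2.5% point of Beta(x, n − x + 1) and the 97.5% point of Beta(x + 1, n − x).

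| Alive / n | Rate | Exact 95% CI |
|---|---|---|
| 43/61 | 70.5% | 57.4% to 81.5% |
| 49/61 | 80.3% | 68.2% to 89.4% |
| 55/61 | 90.2% | 79.8% to 96.3% |
| 58/61 | 95.1% | 86.3% to 99.0% |

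The number on 100/20 is not stated. If it is about half of the 47 interim patients (assume 23), the normal approximation at 80% gives 1.96 × √(0.8 × 0.2 / 23) = 0.163, against 1.96 × √(0.8 × 0.2 / 61) = 0.100 for 61 patients. Censoring would widen all of these.

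**The case against.** The strongest reply is that this is an openly abbreviated close-out plan. OS was not singled out: the hypothesis tests, the investigator-assessed endpoints, the change in SPD and the quality-of-life outputs also went. The omission is stated in plain words, early termination is given as the cause, and every death is listed with date and cause. A crude death count with follow-up could be reported from the planned outputs. An OS curve might be heavily censored, and no primary conclusion depends on it.

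Most of that stands, and it rules out several stronger readings that a reader might infer:

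- *That mortality survives only as a listing.* It does not; deaths also enter PFS, DoR, the graded TEAE table to Day 92 and probably disposition.
- *That many deaths go unsummarised.* Neither document gives a death count, so this cannot be said.
- *That OS was removed because of what the July 2022 review of 61 patients showed.* The review is described as an efficacy review of patients with an IRC baseline and 3-month scan. Nothing says that survival was examined.
- *That the omission hides the secondary-malignancy risk.* OS does not measure that risk, and the SAP handles it through AESI review and flagging.

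What the reply does not answer is why PFS is kept to 15 months with a plot while OS, whose dates are already specified, is not estimated. Early termination applies equally to both.

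**Conclusion.** The point holds as a reporting gap that is cheap to close. OS is a Part B secondary endpoint, the SAP does not derive it, Section 3.10 gives no OS-specific reason, and Section 3.5.2 already specifies the event and censoring times. No retained output replaces it: a death after progression enters no time-to-event estimate, and a death after two or more missed scans is censored in PFS.

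The gap affects the completeness of the final report, not the primary ORR result, and the documents do not support a charge of selective reporting. The gain is also bounded. For 40/15, an assumed 80% landmark rate in 61 patients without censoring would carry an exact 95% interval of about 68% to 89%. That is imprecise but informative. The 61 are the scan-evaluable patients in the July 2022 review, not necessarily all those treated. The 100/20 estimate would be less precise, at roughly ±16 points if that group numbers about 23.

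**What to change.** In the SAP Introduction, replace the sentence on OS with text such as: OS will be derived from the dates in Section 3.5.2, censoring patients not known to have died at the latest date known alive. It will be summarised by Kaplan-Meier in the Efficacy Analysis Set for 40/15 and 100/20, giving deaths, number censored, numbers at risk, median if reached, landmark rates only where follow-up supports them, and 95% confidence intervals. Label the result descriptive and immature.

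Add OS to SAP Sections 2.2 and 2.3, and record in Section 3.10 that it is reported descriptively after early termination. If the sponsor still prefers not to estimate OS, the minimum is an OS-specific reason in Section 3.10 and a table of deaths by regimen.

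The cost is one table and one figure from variables already specified. The downside is wide intervals and censoring, which the labelling should make plain.

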2.1 Study Design

Part B of the LYMRIT-37-01 study started as a randomised phase IIb, open-label, study in participants with relapsed, rituximab/anti-CD20 refractory Follicular Lymphoma (FL), platelet count $\geq 150 \times 10^9$ /L and having received 2 or more prior chemotherapy or immunotherapy-based regimens.

In Part B, per initial design, up to 130 participants were to be enrolled in a 1:1 randomised fashion to compare the recommended phase II dose of Arms 1 and 4 (40 mg lilotomab + 15 Mega Becquerel (MBq)/kg Betalutin (“40/15”) vs 100 mg/m² lilotomab + 20 MBq/kg Betalutin, (“100/20”). Following an interim analysis of efficacy and safety data randomisation was stopped and further patients were recruited to “40/15” regimen (as recommended by the SRC).

The eligibility criteria for Part B, were widened (under protocol version 14), to allow enrolment of participants with prior autologous-SCT (that occurred more than 2 years prior to enrolment in the study) and/or with platelet counts $\geq 100 \times 10^9$ /L but $< 150 \times 10^9$ /L at study entry. These patients received a reduced dose regimen: “40/12.5” or “40/10”.

Part C of the LYMRIT-37-01 study was added in Protocol version 15.1 (EU&RoW) and Protocol version 15.2 and is an open-label phase IIa expansion cohort in participants with relapsed iNHL to enable the collection of samples for Betalutin PK and total lilotomab antibodies PK in receiving the “40/15” dose regime.

Full detail of the study design is provided in the protocol Section 6.

2.1.1 Visit Structure

The visit structure and the schedule of assessments are detailed in Tables 6-7, 6-8 and 6-9 in the study protocol (Section 6).

In the protocol, the Betalutin administration day is referred to as Day 0. However, for statistical analysis and to be in line with CDISC (Clinical Data Interchange Standards Consortium) requirement, the Betalutin administration day will be defined as study Day 1. See Section 3.3 for more details.

The study treatment period starts with the single dose infusion of rituximab (375mg/m²) 14 days prior to the administration of Betalutin and lasts for 12 weeks after the Betalutin administration for each participant.

The follow-up period starts from 12 weeks (3 months or 92 days) after the first lilotomab/Betalutin administration up to 5 years as follows (see Protocol Section 6.3 Schedule of Assessments for more details):

- Extensive follow-up (hospital visits): for all participants, every 3 months after Betalutin administration for the first year (i.e. Month 3, Month 6, Month 9, and Month 12). In addition, there will be an additional hospital visit at Week 4 and Month 2 after Betalutin administration. Tumour imaging assessments are only required until the participant has disease progression as confirmed by the IRC or further anticancer therapy prior to progression. All other scheduled assessments are performed regardless of disease progression or administration of further therapy.
- After Month 12: follow-up will continue every 6 months up to 5 years after the Betalutin dose.
 - Extensive follow-up (hospital visits) will be performed until the participant has disease progression as assessed by the IRC or further anticancer therapy prior to progression.
 - Survival Follow-up: Thereafter, the participant will continue limited follow up every 6 months for potential long-term toxicity (new onset of Adverse Events of Special Interest (AESIs), Adverse Drug Reactions (ADRs) and study treatment-related Serious Adverse Events (SAEs), Overall Survival, further anticancer treatment and immunogenicity assessment (ADA, if applicable). Unless blood sampling is required for immunogenicity, limited follow-up visits can be performed by telephone.

A visit window of ± 2 days is permitted for the nominal Day 0 visit (the dose of radioactivity will be based on the actual administration date). Weekly assessments should occur within a window of ± 2 days. Visits occurring at 4-week intervals will have a window of ± 3 days. During the treatment and follow-up period, a window of ± 7 days for visits occurring every 3 or 6 months is acceptable.

All samples/assessments for study baseline are to be obtained before rituximab dosing. The associated results will be used for Betalutin treatment baseline except for haematology, which is to be repeated within 72 hours prior to Betalutin administration and will be used as the Betalutin baseline.

